### **Additional objectives**

Further outcomes will be described in Section 9.3.2.2 of the protocol.

Collection of serious and non-serious adverse drug reactions and fatal adverse effects during the whole NIS (52 weeks) and reporting according to relevant SOP.

This is the first RWE study in patients suffering from chronic fibrosing ILD with a progressive phenotype in Germany being treated with nintedanib. In addition, the German healthcare system is currently strongly supporting all necessary activities to fight the global Covid-19 pandemic with possible effects on the conduct of this study. In order to be able to identify and counteract possible restrictions due to these circumstances, a descriptive snapshot analysis is planned at the time of Last Patient In (LPI) in this study.

## **9. RESEARCH METHODS**

### **9.1 STUDY DESIGN**

Single-arm, open-label observational cohort study according to §4, section 23 and §67, section 6 German Medicines Act (NIS): All included chronic fibrosing ILD with a progressive phenotype patients will receive treatment with nintedanib for approximately 52 weeks. NIS based on newly collected data.

Primarily, this study aims to observe the course of FVC, dyspnea- and cough scores in the L-PF questionnaire over 52 weeks of nintedanib treatment in patients suffering from chronic fibrosing ILD with a progressive phenotype (but not IPF) and investigate possible correlations between

- Correlation between change from baseline to week 52 in FVC [% pred.] and change from baseline to week 52 in dyspnea symptom score; safety issue: no
- Correlation between change from baseline to week 52 in FVC [% pred.] and change from baseline to week 52 in cough symptom score; safety issue: no

from each individual patient's difference between baseline and after 52 weeks of treatment with nintedanib. Secondary objectives are change in L-PF cough and dyspnea symptom scores over time.

- Correlation between change from baseline to week 52 in FVC [mL] and change from baseline to week 52 in dyspnea symptom score; safety issue: no
- Correlation between change from baseline to week 52 in FVC [mL] and change from baseline to week 52 in cough symptom score; safety issue: no
- Absolute change from baseline in L-PF cough symptom score at week 52
- Absolute change from baseline in L-PF dyspnea symptom score at week 52

In Germany, more than 99.9 % of citizens are health insured and usually treatment expenses for approved drugs are covered by the health insurance. Therefore, patients receive treatment, except those unwilling to be treated. Those patients are very rare and not suitable as a control group. As Nintedanib is the first treatment approved in Germany in this indication, a comparator arm is not feasible. As treatment is available, a NIS with a placebo group will not get ethical approval in Germany.

Patients recruited for this non interventional study will be treatment-naïve for prior antifibrotic treatment. This will allow to collect clinical baseline data before starting any therapy. After 52 weeks, we will be able to compare these baseline data with the data collected while on nintedanib treatment at the study visits for up to 52 weeks. However, it should be mentioned that due to the natural course of the disease, FVC is expected to decline during the study for the population. As an untreated or placebo group is not planned for due

to ethical reasons, this limitation needs to be considered. However, efficacy and safety of nintedanib have been well established in the RCT INBUILD, also in comparison to placebo. Among others the following will be analyzed:

- comparison of patient data at baseline (patients have no prior antifibrotic treatment) vs data after 52 weeks of nintedanib treatment.
- comparison of the correlation  $\Delta FVC$  and  $\Delta$ cough/ $\Delta$ dyspnea in the first 26 weeks with vs correlation  $\Delta FVC$  and  $\Delta$ cough/ $\Delta$ dyspnea in the last 26 weeks.

This approach will allow for comparison between patients untreated and patients after up to 52 weeks of nintedanib treatment as well as during the first and second half year of treatment.

## **9.2 SETTING**

In this NIS, data on the effect of a nintedanib in chronic fibrosing ILD with progressive phenotype in about 100 patients will be collected in routine clinical practice by ca. 20 specialists, experienced in treating ILD patients, (e. g. pulmonologists and rheumatologists) throughout Germany. Each investigator will include ca. 5 consecutive patients for whom the physician had decided on a nintedanib treatment before.

Per definition, non-interventional studies do not include any randomization. In this study, there will be no procedure outside routine clinical practice. Patients will be recruited for this study only after a physician's therapeutic decision to treat the individual patient with nintedanib.

For ethical and/or medical reasons, patients with contraindications (CI) to nintedanib according to SmPC, including pregnant or lactating women, current cancer patients, patients not willing to consent and patients being spouse or lateral relatives to the second degree or economically dependent from the investigator will be excluded.

All calculations for this study, including statistics and patient numbers, are based on the randomized clinical trial INBUILD. In order to be able to duplicate the most crucial design features, in this study nintedanib will solely be tested as a first and only antifibrotic treatment in PF-ILD patients, as it was in INBUILD. Therefore, in accordance with INBUILD trial design, patients must not have used or use any antifibrotic before or during this observational study apart from nintedanib.

This study is planned to observe patients for 12 months. Therefore, patients with a life expectancy of 12 months or less should not be included. As acute exacerbations severely impact life expectancy, patients with acute ILD exacerbations should not be included in the study.

Patients must not participate in a parallel interventional clinical trial for not to interfere with the study aims and outcomes.

The impact of excluding those patients seems low, as the number is expected to be minimal and patients with contraindications in any case would not be treated with nintedanib.

### **9.2.1 Study sites**

Data collection of approximately 100 patients from approximately 20 recruiting sites, experienced in treating ILD patients, (e. g., pulmonologists and rheumatologists) throughout Germany is planned. Site selection will be performed to reflect routine care for chronic fibrosing ILD patients with a progressive phenotype in Germany in order to secure representativeness of this specific ILD population.

### **9.2.2 Study population**

#### Indication

Patients to be recruited within this study have to have a physician diagnosed chronic fibrosing ILD with a progressive phenotype (except IPF), for which nintedanib is an indicated treatment.

Before visit 1, patients must not have been treated with either nintedanib or pirfenidone, i. e., all patients are considered treatment naïve with regard to these antifibrotic treatments.

- Only patients, for whom their treating physician has made the clinical decisions to start nintedanib treatment (but not actually started treatment) independently of this study, are eligible to enter the study.
- During the study, all patients are treated with nintedanib according to standard of care. For each individual patient, a treatment observation period of 52 weeks is aimed for. Handling of patient data with shorter observation period is going to be described in the SAP.

#### Inclusion criteria

- Adults  $\geq$  18 years at Visit 1
- Subjects must be contractually capable and mentally able to understand and follow the instructions of the study personnel
- Physician's diagnosis of chronic fibrosing ILD with a progressive phenotype, except IPF
- Treatment with nintedanib in INREAL will be the first and only prescription of any antifibrotic treatment for each individual patient within this observational study after a physician's decision being made for this treatment option earlier
- Outpatients not currently hospitalized with a life expectancy  $>$  12 months per investigator's assessment
- Written informed consent prior to study participation
- Current FVC measurement (taken within the last 3 months) available in the patient file
- Women of childbearing potential must take appropriate precautions against getting pregnant during the intake of nintedanib.

**Exclusion criteria**

- Patients with contraindications acc. to SmPC
- Prior use of any antifibrotic treatment
- Lack of informed consent
- Pregnant or lactating females
- Any physician diagnosed exacerbation of ILD in the patient's history file, irrespective of time since event
- Current diagnosis of lung cancer
- Respiratory failure (pH < 7,35 and/ or respiratory rate > 30/min) in the patient's history
- Participation in a parallel interventional clinical trial
- Patients being spouse or lateral relatives to the second degree or economically dependent from the investigator

Recently, an ILD incidence rate of 20–30 per 100,000 person-years was suggested for populations across Europe.

Suitable patients shall be included consecutively at the sites. Patient selection and proposition of study participation by the investigator will be conducted independently from the treatment decision and after the treatment decision has been agreed between the treating physician and the patient.

If the patient is interested in study participation, the treating physician will explain the study details including the nature and importance of the study and its impact on health and potential risks, both orally and in writing. The patient will have ample time to read the information, ask questions and consider study participation before giving written informed consent.

For more details see sections [9.2.3](#) (Study Visits) and [10.1](#). (STUDY APPROVAL, PATIENT INFORMATION AND INFORMED CONSENT).

A subject screening log will be kept at the site or in the study electronic portal, recording basic information (e.g. initials, gender, date of birth, reason for not enrolling the patient etc.) on all patients who were invited to participate in the study, with information on the eligibility (or reasons for non-eligibility) and date of signed informed consent, if applicable. In the case of refusal, reasons for refusal should be given. In addition, a log of all patients included into the study (i.e. having given informed consent) will be maintained in the main study file at the study site.

**9.2.3      Study visits**

In this NIS, data on the effect of a treatment with nintedanib on differences in cough and dyspnea scores, measured via the L-PF questionnaire, will be collected and this information will be assessed in relation to FVC from these patients' medical files in patients with chronic fibrosing ILD with a progressive phenotype.

Four visits are mandatory within this study:

V1 – baseline visit

V3 – mid-observation period

planned visit date: 26 weeks after V1

must not take place earlier than week 20 or later than week 32 after V1

V5 – end of observation

planned visit date: 52 weeks after V1, must not take place earlier than week 46 or later than week 58 after V1

V6 – Follow-up 52 weeks after start of treatment

Each of these visit should take place not earlier than six weeks before and not later than six weeks after the planned visit date (V1 + 26 weeks; V1 + 52 weeks) and thus reflect patients' and physicians' real-world experience.

In addition to Visits 1, 3 and 5 described here, optional study visits will be enabled between V1 and V3 as well as between V3 and V5, each occurring about midway between V1 and V2 or V2 and V3, respectively. Optional visits should take place

optional Visit V2: planned visit date week 13 after V1

if applicable, V2 must not take place earlier than week 7 or later than week 20 after V1

optional visit V4: planned visit date week 39 after V1

if applicable V4 must not take place earlier than week 33 or later than week 45 after V1

When optional visits are conducted, then the same parameters as in Visit 3 should be documented.

Therefore, patients will be seen by their investigator at least every 6 months and up to every quarter of the observational period.

The baseline visit will take the patients ca. one hour including filling out the questionnaires, visits 2 to 6 will take about 30 minutes each. All data documented during those visits, including the questionnaires, record examinations and information necessary during the course of the disease and nintedanib treatment.

If possible, patients who discontinue the study before week 52 for any reason should be contacted for survival status and follow-up data at week 52, as available (Visit 6). A phone contact with the patient / relatives / family doctor is acceptable for V6.

So, the time needed by the patient for the whole study depends on the number of visits performed. The duration of each visit depends on the amount of data to be collected and the possible questions to be discussed between investigator and participant. For baseline, we

presume about one hour, for the following visits about 30 minutes including filling out the questionnaire.

All details on the data collected and tasks performed at each visit are shown in [table 9.2.3: 1](#).

Table 9.2.3: 1 Flow Chart

Parameter	Visit 1; baseline visit	Visit 2; (optional) ca. week 13	Visit 3; mid of observa- tion; ca. week 26*	Visit 4; (optional) ca. week 39	Visit 5; end of observa- tion; ca. week 52	Visit 6 FU ca. week 52**
Informed Consent	X					
Inclusion / Exclusion Criteria	X					
Patient demographics (age, gender, height, and weight)	X					
Smoking history	X					
History of ILD, including ILD entity and HRCT pattern (where available in patient documentation)		X				
current DLCO measures (where available in patient documentation)	X	X	X	X	X	
Concomitant diseases / Comorbidities	X	X	X	X	X	
Past ILD therapies (6 weeks before visit 1)	X					
Current ILD related or other relevant concomitant medication	X	X	X	X	X	
FVC (mL and % pred.; if available in patient data)	X	X	X	X	X	X
Severity of disease as per the treating physician's estimation (if available in patient data)	X	X	X	X	X	X
L-PF questionnaire, completed by patient	X	X	X	X	X	X

Table 9.2.3: 1 (cont'd)

Flow Chart

Parameter	Visit 1; baseline visit	Visit 2; (optional) ca. week 13	Visit 3; mid of observa- tion; ca. week 26*	Visit 4; (optional) ca. week 39	Visit 5; end of observa- tion; ca. week 52	Visit 6 FU ca. week 52**
Safety: Adverse Drug Reactions (serious and non-serious), fatal AEs, pregnancy	X	X	X	X	X	X
Rationale for treatment discontinuation (if applicable)		X	X	X	X	
Further treatment options yes/no (as applicable)		X	X	X	X	X
Intention to continue or discontinue treatment with nintedanib after the study (yes/no)		X	X	X	X	
Survival data						X

\* after 26 weeks of observation for each individual patient

\*\* if available and/or patients willing to perform, phone contact acceptable

In addition to the mandatory visits, i.e. Visit 1 (baseline), Visit 3 (mid of observation; 26 weeks after baseline) and Visit 5 (end of observation) and Visit 6 (Follow-up 52 weeks after baseline), optional study visits will be enabled between V1 and V3 (V2) as well as between V3 and V5 (V4), each occurring about midway between V1 and V3 or V3 and V5, respectively. Therefore, patients will be seen by their study investigator at least every 6 months and up to every quarter of the observational period.

When optional visits are conducted, then the same parameters as in Visit 3 should be documented.

Each visit should take place not earlier than six weeks before and no later than six weeks after the planned visit date and thus reflect patients' and physicians' real-world experience.

If possible, patients who discontinue the study before week 52 for any reason should be contacted for survival status and follow-up data to week 52 (visit 6).

For all other patients, visit 5 and visit 6 are completed in the same visit.

#### **9.2.4 Study discontinuation**

Boehringer Ingelheim reserves the right to discontinue the study overall or at a particular study site at any time for the following reasons:

1. Failure to meet expected enrolment goals overall or at a particular study site
2. Emergence of any effectiveness/safety information that could significantly affect continuation of the study
3. Violation of Good Pharmacoepidemiology Practice (GPP), the study protocol, or the contract by a study site, investigator or research collaborator, disturbing the appropriate conduct of the study

The investigator/the study site/research collaborator will be reimbursed for reasonable expenses incurred in case of study/site termination (except in case of the third reason).

The patients have the right to stop study participation any time and for any reason, without any drawback on their further treatment. Study participation may be stopped for a given patient in case of individual safety issues.

### **9.3 VARIABLES**

The following parameters will be collected and assessed at visits 1 to 5, as applicable:

- Patient demographics (age, gender, height, weight)
- Smoking history, current status (current smokers, former smokers, and never smokers) and pack-years
- History of ILD, including ILD entity and HRCT pattern (where available in patient documentation)
- current DLCO measures (where available in patient documentation)
- Concomitant diseases
- Previous ILD therapies in the 6 weeks before visit 1
- Current ILD related or other relevant concomitant medication
- FVC (mL and % pred.; if available in patient data)
- Severity of disease as per the treating physician's estimation (if available in patient data)
- L-PF questionnaire, completed by patient
- Safety: ADRs (serious and non-serious), fatal AEs, pregnancies during the study
- Rationale for treatment discontinuation (if applicable)
- Intention to continue or discontinue treatment with nintedanib (Ofev®) after the study (yes/no)
- Further treatment options yes/no, as applicable

### **9.3.1 Exposures**

The active ingredient of Ofev® is nintedanib. During this study, it is planned to observe for each patient a treatment period with nintedanib of approximately 52 weeks.

The recommended daily dose of nintedanib (Ofev®) is 150 mg twice daily administered approximately 12 hours apart. The 100 mg twice daily dose is only recommended to be used in patients who do not tolerate the 150 mg twice daily dose.

The treating physician ensures that the treatment follows all specific requirements described in the SmPC as e.g. contraindications including pregnancy, monitoring, discontinuation, dose reduction etc.

The Summaries of Product Characteristics on Ofev® is contained in the NIS ISF in the “Summary of Product Characteristics” section.

Note: The recommended doses stated in the Summary of Product Characteristics should not be exceeded.

Other adequate therapy will be applied according to label as described in the respective SmPCs.

The study aims to observe for each patient a treatment period with nintedanib of approximately 52 weeks (including a mid-of-observation evaluation and 2 further optional intermediate visits). As there is no untreated comparator group, each patient included in the study is planned to be continually exposed to nintedanib as a standard of care for the whole observational period of 52 weeks at the indicated dosage of 150 mg daily. As this is a real-world observational study, patients will be instructed on the correct drug application by their treating physician. In case of dose reductions deemed necessary by the treating physicians, these may be applied according the SmPC. All cases of dose reduction or dose interruption will have to be documented and reasons given in the eCRF.

A dose interruption of nintedanib for more than 12 weeks and/or initiation of another antifibrotic therapy during the observation phase of the study will result in exclusion of the concerned patients' data from efficacy analysis.

Handling of missing data will be described in the SAP.

Exposure variables will be cough score and symptoms score as measured via L-PF questionnaire.

The complete L-PF questionnaire will be collected by the site in an eCRF. Each question is answered by the patient indicating one tick-box answer per question. Only one statement can be chosen. The higher the score the greater the impairment.

Ofev® (Nintedanib) is authorized in Germany for the treatment of adult patients suffering from chronic fibrosing ILD with a progressive phenotype as Ofev®. Each patient in need and meeting the criteria defined in the SmPC may get an Ofev® prescription by the treating physician. Statutory health insurances in Germany cover Ofev® prescription costs.

Furthermore, Ofev® is also indicated to treat adults with idiopathic pulmonary fibrosis (IPF), systemic sclerosis associated interstitial lung disease (SSc-ILD), and other chronic fibrosing interstitial lung diseases which are progressive.

This study aims to continually observe adult patients suffering from chronic fibrosing ILD with a progressive phenotype who are newly treated with nintedanib without any previous antifibrotic therapy, i. e. neither pirfenidone nor nintedanib, for 52 weeks. Neither switchers nor past or current users of nintedanib (or pirfenidone) are to be included. Based on the INBUILD study, this study is planned in a parallel way. It is assumed that PROs will be determinable best in new users. All calculations for this study, including statistics and patient numbers, are based on the randomized clinical trial INBUILD. In order to be able to duplicate the most crucial design features, in this study nintedanib will solely be tested as a first and only antifibrotic treatment in PF-ILD patients, as it was in INBUILD. Therefore, in accordance with INBUILD trial design, patients must not have used or use any other antifibrotic before or during this observational study, except nintedanib during the study.

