### **9.7.3 Safety Analysis**

All adverse drug reactions (ADRs) (serious and non-serious) and all AEs with fatal outcome as collected per study protocol will be included and summarised in the final study report.

Adverse events will be coded using the Medical Dictionary for Regulatory Activities (MedDRA) coding dictionary. Standard BI summary tables and listings will be produced. All treated patients will be included in the safety analysis. In general, safety analyses will be descriptive in nature and will be based on BI standards. No hypothesis testing is planned.

Kaplan-Meier plots will be produced for the time to premature treatment discontinuation, for the time to first dose reduction and for the time to first treatment interruption.

Statistical analysis and reporting of adverse events will concentrate on treatment-emergent adverse events. To this end, all adverse events occurring between start of treatment and end of the residual effect period will be considered 'treatment-emergent'. The residual effect period is defined as the 28 days after the date of the last dose of study medication. Adverse events that start before first drug intake and deteriorate under treatment will also be considered 'treatment-emergent'.

Frequency, severity, and causal relationship of adverse events will be tabulated by system organ class and preferred term after coding according to the current version of MedDRA.

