## 6.3 STUDY POPULATION

### Indication

Patients to be recruited within this study have to have a physician diagnosed chronic fibrosing ILD with a progressive phenotype (except IPF), for which nintedanib is an indicated treatment.

Before visit 1, patients must not have been treated with either nintedanib or pirfenidone, i. e., all patients are considered treatment naïve with regard to these antifibrotic treatments.

- Only patients, for whom their treating physician has made the clinical decisions to start nintedanib treatment (but not actually started treatment) independently of this study, are eligible to enter the study.
- During the study, all patients are treated with nintedanib according to standard of care. For each individual patient, a treatment observation period of 52 weeks is aimed for. Patient's data with shorter observation period will be analyzed up to the date of data collection of the corresponding patient.

Inclusion and exclusion criteria are listed in section 9.2.2 of the Study Protocol as of 8 FEB 2021. Exclusion criterion 4 was changed in Local Amendment 1.0 dated 20 JAN 2022.

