**Time to premature treatment discontinuation:** Time to premature treatment discontinuation is defined as the time from first dose of nintedanib until date of premature treatment discontinuation of nintedanib. The calculated time for patients without premature treatment discontinuation of nintedanib will be censored at the date of last contact.

**Time to first dose reduction:** Time to first dose reduction is defined as the time from first dose of nintedanib until the start date of first dose reduction to 100 mg/ twice daily or to other dose/ frequency excluding treatment interruption with 0 mg nintedanib administration daily. The calculated time for patients without dose reduction of nintedanib will be censored at the date of last contact.

**Time to first treatment interruption:** Time to first treatment interruption is defined as the time from first dose of nintedanib until the start date of first treatment interruption with 0 mg nintedanib administration daily. The calculated time for patients without treatment interruption of nintedanib will be censored at the date of last contact.

**Treatment-emergent adverse events (TEAE):** All adverse events occurring between start of treatment and end of the residual effect period will be considered 'treatment-emergent'. The residual effect period is defined as 28 days after the date of the last dose of study medication. Adverse events that start before first drug intake and deteriorate under treatment will also be considered 'treatment-emergent'.

**Change from baseline to week 52 in FVC [% pred.]:** FVC [% pred.] at week 52 – FVC [% pred.] at baseline

**Change from baseline to week 52 in FVC [mL]:** FVC [mL] at week 52 – FVC [mL] at baseline

**Change from baseline to week 52 in L-PF dyspnea symptom score:** L-PF dyspnea symptom score at week 52 – L-PF dyspnea symptom score at baseline

**Change from baseline to week 52 in L-PF cough symptom score:** L-PF cough symptom score at week 52 – L-PF cough symptom score at baseline

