## 7.1 Exposures

As there is no untreated comparator group, each patient included in the study is planned to be continually exposed to nintedanib as a standard of care for the whole observational period of 52 weeks at the indicated dosage of 150 mg twice daily. As this is a real-world observational study, patients will be instructed on the correct drug application by their treating physician. A dose interruption of nintedanib for more than 12 weeks and/or initiation of another antifibrotic therapy during the observation phase of the study will result in exclusion of the concerned patients' data from efficacy analysis.

Exposure variables will be cough score and symptoms score as measured via L-PF questionnaire.

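### Does the planned-exposure sentence in Protocol 9.3.1, which gives a different daily dose from the rest of its section and from SAP 7.1, call for a change to the plan?

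*Protocol*

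**What the plan says.** Protocol 9.3.1 (Exposures) makes two statements about the regimen. Early on it says that the recommended dose "is 150 mg twice daily administered approximately 12 hours apart", and adds: "The 100 mg twice daily dose is only recommended to be used in patients who do not tolerate the 150 mg twice daily dose". Further down it says that each patient is planned to be exposed continuously "for the whole observational period of 52 weeks at the indicated dosage of 150 mg daily". It then turns to dose changes: "In case of dose reductions deemed necessary by the treating physicians, these may be applied according the SmPC". Every reduction or interruption is to be recorded in the eCRF with its reason.

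SAP 7.1 (Exposures) carries almost the same planned-exposure sentence, but it reads "for the whole observational period of 52 weeks at the indicated dosage of 150 mg twice daily".

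One planned output concerns dose level. Protocol 9.7.3 and SAP 10.3 call for Kaplan-Meier plots, among them plots "for the time to first dose reduction and for the time to first treatment interruption". SAP section 7 ends the first of these intervals at "the start date of first dose reduction to 100 mg/ twice daily or to other dose/ frequency", leaving out interruptions at 0 mg.

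**The concern.** A dose statement that differs by a factor of two within one section, and again between protocol and SAP, deserves attention wherever it appears. Here it appears in the section that defines exposure. It is complete running prose, so it is not a broken table or a redaction. The protocol's list of amendments and the SAP's history table mention no change to either sentence, so neither document explains the difference.

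Two things could be at stake. A site might take the sentence as an instruction. Or the reference point for a dose reduction might become unclear: the step that the protocol reserves for patients who do not tolerate 150 mg twice daily is a larger daily total than the planned exposure read literally. If that ambiguity reached the data, the time to first dose reduction would be affected.

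**Working it through.** **Size of the mismatch.** Daily total = amount per administration × administrations per day.

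| Statement | Source | Daily total |
|---|---|---|
| 150 mg twice daily, recommended | Protocol 9.3.1, early | 150 × 2 = 300 mg |
| 100 mg twice daily, if not tolerated | Protocol 9.3.1, early | 100 × 2 = 200 mg |
| 150 mg daily, planned exposure | Protocol 9.3.1, later | 150 × 1 = 150 mg |
| 150 mg twice daily, planned exposure | SAP 7.1 | 150 × 2 = 300 mg |

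The two planned-exposure sentences differ by 300 / 150 = 2.0. The 200 mg step is 200 / 300 = 0.67 of one total and 200 / 150 = 1.33 of the other. Read literally, the wordings are not equivalent.

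**Does the sentence govern treatment?** The protocol does not assign a dose. Protocol 9.2 and 9.2.2 admit patients only after the physician has decided on nintedanib, and 9.2 excludes any procedure outside routine practice. Protocol 9.3.1 makes the physician responsible for following the SmPC, which is kept in the site file, and section 10 leaves standard care with the physician. The sentence describes what is expected under standard of care. It is not a dosing instruction.

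**Does any analysis use the sentence?** Taking each in turn:

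- *Co-primary and secondary correlations* (SAP 10.1): Pearson coefficients between change in FVC and change in L-PF score. No dose term.
- *Sample size* (Protocol 9.5): an assumed correlation of about -0.3, two-sided 0.05, 80% power and about 15% drop-out, giving 84 evaluable and 100 recruited. No dose term.
- *Repeated-measures models* (SAP 10.1): visit, baseline and their interaction. The covariates in SAP 7.3 are baseline DLCO and FVC. No dose term.
- *Efficacy exclusion rule* (Protocol 9.3.1, SAP 7.1) and *per protocol set* (SAP 10): interruption beyond 12 weeks, another antifibrotic, missing data, and entry criteria. No dose level.
- *Time to first dose reduction* (SAP 7): identified by the step to which the dose is reduced, and by recorded start dates. The definition does not cite the protocol sentence, and it fits the regimen in the SAP's own section 7.1. The safety analyses are descriptive, with no hypothesis testing.

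So the number of planned estimates or tests that take the disputed figure as an input is zero.

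**The case for a change.** The best case for acting is that a protocol should not leave a dose to inference, particularly when the repair is one phrase. It can be added that sites record reductions against some reference regimen, that the protocol gives two, and that the SAP definition fits only one of them.

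Part of this stands. The texts do conflict, and they must be reconciled. The section's habit of giving a per-administration amount under a daily-dose label suggests loose drafting, but it does not remove the conflict. It is also fair that the word reduction implies a starting point, and that the SAP definition does not fit the literal protocol sentence.

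The rest does not carry the case. Reductions are made by the physician under the SmPC and recorded as they happen, so they can be counted without the disputed sentence. Nothing in the documents suggests that a site was misled. A separate notice to sites is therefore not supported. On the planned timetable it would also have come late: the final SAP is dated 17 November 2022, and data collection was due to end in February 2023. The silence of the change logs shows only that no change was recorded.

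It is also not known whether the sentence still stands. SAP 6.3 notes that "Exclusion criterion 4 was changed in Local Amendment 1.0 dated 20 JAN 2022", and the SAP history records a changed protocol version. That later protocol text is not among the documents reviewed.

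**Conclusion.** The inconsistency is genuine and clerical. Taken literally it is twofold (300 against 150 mg per day), but its effect on the correlations, the sample size, the analysis sets and the models is nil. The one dose-related output is a descriptive plot whose definition works from recorded reductions. No change to design, analysis or conclusions follows.

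The two statements in Protocol 9.3.1 must be reconciled with each other, with SAP 7.1 and with the product information that the protocol cites. That is housekeeping for the next protocol update, if the sentence survives in the current text. No view is taken on which wording is right.

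The conclusion rests on two assumptions: that prescribing followed the SmPC under the treating physician, as the protocol says, and that reductions were entered in the eCRF as required. If sites had instead used the sentence as a dosing instruction or as the reference for recording reductions, the dose-reduction plot would need a second look. The documents give no sign of either.
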